5 RISKS AND BENEFITS OF OTL38

5.1.1 Risks

The issues of possible concerns with the use of the OTL38 and the imaging system are:

- Presence of an imaging system in the operating room
- Phototoxicity or thermal damage from the light source
- Nonspecific localization of OTL38
- Failure of OTL38 to bind to receptors
- Fading of the chromophore (photobleaching)
- Inability to excite the dye in OTL38 or to record emission
- Adverse events suggestive of hypersensitivity

5.1.1.1 *Imaging system*

The presence of an imaging system in the operating room is not novel and should not create a problem with maintaining a sterile field. In this case, the camera system will be used for intra-operative imaging prior to surgical resection to record the localization of tumors, and post-resection to document the visualization of any residual tumor. As such, it need not be intrusive during the procedure. Standard operating room procedures to ensure a sterile milieu, including appropriate draping of the imaging system, will be employed.

There is a potential for phototoxicity or thermal damage from any light source. The degree of risk is related to the power of the light, the duration of exposure, and the temperature of the light source near the patient. The maximum temperature and irradiance for the imaging system are well within established safety limits. Controls will be in place to ensure that the exposure to the imaging system is limited to that is necessary to identify the tumor lesions and capture images.

Like all chromophores (fluorophores), excitation by appropriate wavelength of light will result in molecular activation resulting in a different wavelength of light being emitted. This is an active process that changes the excitability of the molecule potentially leading to photobleaching. Since white light contains all wavelengths of light, extended room light exposure could lead to bleaching. Exposure to the excitation light source will be limited during the procedure. According to van Dam et al. (2011), the initial images can be captured in a mean time of 10 minutes (4-36 minutes), and tumor-specific fluorescence can be detected for up to 8 hours. The risk that the camera system will not excite the OTL38 dye or record an image after emission is minimal.

5.1.1.2 *OTL38*

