 - Begin administration of study medication less than 2 hours prior to the skin incision on day of surgery in the preoperative area.
 - Record time of study medication administration
 - Record time of scheduled surgery (listed operating room time)
- AE assessment: including hypersensitivity reactions, which could include skin reactions, difficulty breathing, eye or nasal reactions, or gastrointestinal complaints, redness, tenderness, pain, or rash at the injection site or any clinically relevant abnormality (with exception of surgical scars) noted after the start of the study medication that was not present at screening.

8.3.2.2 Surgery:

The da Vinci[®] Fluorescence Imaging Vision System, SPY Elite Imaging System or Visionsense VSiii 3DHD system will be used to identify tumor lesions under normal/visible light and fluorescent light prior to surgical excision of lesions, and again after surgical excision of lesions to identify persistent lesions. The da Vinci system or Visionsense VSiii system will be used for all partial nephrectomies (robotic) and for robotic radical nephrectomies. The SPY Elite will be used for open radical nephrectomies. See **Appendix D** and **Appendix E** for more detailed information about the da Vinci and SPY camera/imaging systems. Information about the Visionsense VSiii system can be found at <http://www.visionsense.com/vsiii-system/>.

The Investigator will record the start and stop time for each exposure to fluorescence (pre-resection, post-initial resection, other [give reason]) in the eCRF. The total time of fluorescence will be calculated automatically.

Status	Time On Fluorescent Light	Time Off Fluorescent Light
Before surgical excision		
After initial surgical excision		
Other (explain reason)		

The number and location of suspect tumor lesions detected under **normal light and/or by palpation** will be recorded on the schematic (**Appendix B**) using an “O”. The number and location of suspect tumor lesions detected using **fluorescent light** will be recorded on the schematic using an “x” (for those lesions that were also identified under normal light and/or by palpation, the “x” will be superimposed on the “O” as “⊗”; and for those identified only under fluorescence, they will be recorded only by the “x”).

Light source	Notation
Visible light	O
Fluorescent	X
Both	⊗

For Partial Nephrectomies

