12.3 Sample size

The study consists of a total of 20 patients divided equally between two treatment arms that will be studied simultaneously:

- Arm 1: 10- partial nephrectomy for localized RCC (no lymph nodes)
- Arm 2: 10- radical nephrectomy and lymph node dissection for locally advance or metastatic RCC.

A total sample size of 20 was determined to balance the competing goals of assessing the primary and secondary while not exposing more patients to an investigational procedure than is required. Also, there is an 88% probability of seeing at least one toxicity event if the probability of that toxicity is 0.10. Thus, we feel confident that with a sample of size 20, we will be able to detect unacceptable toxicities that have probabilities of 0.10 or higher.

A sample size of 10 for each arm was chosen. If we do not observe sensitivity for detection of RCC of at least 70% in each arm, we will consider further refinement of the methodology before proceeding with additional larger studies.

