12.7 Analysis of primary objective

The primary endpoint is to see if OTL38 and fluorescence imaging has sensitivity to detect RCC in the primary tumor (for partial nephrectomy) or in lymph nodes (for radical nephrectomy with lymph node dissection). Both sensitivity and the secondary endpoint of specificity will be assessed as follows: Final pathology and immunohistochemistry will serve as the gold standard with which gross observation and fluorescent imaging are compared for margin of resection, regional lymph nodes, and primary tumor. Pathology and immunohistochemistry results will be listed per patient. Times on and off for the imaging system will be listed per patient. Sensitivity, specificity, positive predictive value, and negative predictive value will be calculated for descriptive purposes although we understand the sample sizes are not large enough to estimate these values with a high level of accuracy at this stage. That would be accomplished in a future larger study. Sensitivity and specificity will be estimated using the method of Generalized Estimating Equations (GEE), which will take into consideration the correlated nature of multiple lesions removed from the same patient. Each patient will have all excised target lesions contributing to the data analysis (each type: O, x, ⊗, and P).

	Cancer +	Cancer-
Fluorescence+	True Positive (TP)	False Positive (FP)
Fluorescence-	False Negative (FN)	True Negative (TN)

Sensitivity (proportion of true positives) = $(TP/TP+FN) \times 100$

Specificity (proportion of true negatives) = $(TN/FP+TN) \times 100$

Sensitivity will be estimated using the GEE model for binomial distribution with fluorescence (-, +) as the fixed effect and patients as a random effect, and the 95% lower one-sided confidence interval for the true sensitivity will also be estimated. Specificity will be estimated using the GEE model for binomial distribution with fluorescence (-, +) as the fix effect and patients as a random effect, and the 95% lower one-sided confidence interval for the true specificity will also be estimated. Positive and negative predictive value will be estimated using similar methods.

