12.8 Analysis of secondary objectives

Specificity: The analysis for specificity is described above.

Detection of RCC in primary tumor (radical nephrectomy arm only): This analyses will be the same as for the primary objective in the partial nephrectomy arm. Pattern of nodal spread will be described qualitatively.

Agreement between pathological agreement between fluorescence and FR α by IHC: This endpoint will also be assessed by Kappa statistics (for presence/absence) or Intra Class Correlation (for numerical measures). Agreement between nodal and primary tumor fluorescence in the radical nephrectomy arm will be assessed similarly.

Agreement between visual and fluorescent images: Kappa statistics will be used to assess agreement between visual and fluorescent images. In addition, the number of lesions detected by

usual visible/tactile conditions and/or palpation vs fluorescent imaging will be analyzed using a paired t-test.

Inter-observer agreement: Kappa statistics will be used to assess inter-observer agreement between of captured fluorescent images.

Usefulness: Responses to the Likert scale questionnaire completed by the surgeons will be listed and summarized

Safety: Vital signs will be summarized using descriptive statistics. Clinical chemistry, hematology, and urinalysis laboratory values will be listed in tabular format and those with above or below normal range will be identified within the table. AEs and TEAEs will be summarized by body system and presented by severity and causal relationship to study drug. ADEs will be summarized by body system and presented by severity and causal relationship to study device. Patients experiencing serious AEs or serious ADEs will be listed and summarized in tabular format.

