19.4.7 Operation

The da Vinci® Fluorescence Imaging Vision System is used to image OTL38 as follows:

OTL38 is administered 2 to 3 hours prior to scheduled surgery. The agent is rapidly distributed after IV administration and also rapidly eliminated from the circulation. Tissues containing high concentrations of folate receptors sequester the agent.

When illuminated by the NIR excitation light produced by the da Vinci® Fluorescence Imaging Vision System, the tissues containing OTL38 continue to fluoresce while the surrounding tissues become dark. The agent was shown to preferentially label folate-receptor-positive tumors in animal models. Tumors that contain folate receptors will bind OTL38, and the da Vinci® Fluorescence Imaging Vision System will cause the tumors to appear green in the augmented image displayed in the Surgeon Console and on the video monitor. In animal models, tumor-specific fluorescence was shown to last at least 8 hours after administration allowing for post-surgical tumor imaging. Although normal kidney proximal tubule cells contain folate receptors

and uptake of OTL38 in the kidneys is possible, the fluorescence signal in the kidneys is expected to be significantly lower than the tumor tissues ([Ross 1994](#)).

Investigators will employ the device in their procedures as outlined. Once the patient has undergone surgical preparation for a partial nephrectomy and the laparoscope has been inserted into the abdomen, images of the surgical area will be captured using both a fluorescence and white light examination prior to tumor excision. The images will be evaluated to determine the extent of tumor involvement and confirm these assessments with normal visual examinations. Surgery will be performed as per usual protocol/procedure, after which a follow-up image of the surgical field will be captured using fluorescence imaging. The remaining fluorescent tissues will be evaluated for possible tumor involvement and the surgical procedure will be finished as indicated.

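### The paired t-test in section 12.8 compares unconfirmed lesion counts, so benign fluorescent spots alone can produce a significant difference; with 4 or 5 one-lesion differences it can also reach p<0.05 where an exact test does not

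*Combined protocol and SAP*

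**What the plan says.** Section 12.8, under agreement between visual and fluorescent images, plans kappa statistics and then a second analysis: the number of lesions detected under "usual visible/tactile conditions and/or palpation vs fluorescent imaging will be analyzed using a paired t-test". It gives no pathology condition, significance level, sidedness or alternative test. It does not say whether the arms are analysed separately or pooled.

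The surgical procedures in section 8.3.2.2 show what is counted. "The number and location of suspect tumor lesions detected using" fluorescent light are drawn on a schematic, as are those found by normal light or palpation. Lesions found both ways carry a combined mark; "for those identified only under fluorescence, they will be recorded only by the" x. These marks precede any histology.

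Pathology enters in section 12.7: "Final pathology and immunohistochemistry will serve as the gold standard with which gross observation and fluorescent imaging are compared". That section defines false positives and plans sensitivity, specificity and both predictive values on the excised lesions.

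On size, section 12.3 states: "The study consists of a total of 20 patients divided equally between two treatment arms", and "A sample size of 10 for each arm was chosen".

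**The concern.** A test on raw marks cannot tell an extra cancer from an extra benign spot. The protocol itself foresees spots that are not cancer: section 5.1.1 lists "Nonspecific localization of OTL38" among its concerns, section 3.3 notes that normal proximal tubule cells carry the receptor, and Appendix D (section 19.4.7) says "uptake of OTL38 in the kidneys is possible", while expecting a clearly weaker signal there than in tumor. A less specific agent would tend to give a larger count difference and a smaller p-value on this one statistic.

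The second issue is the test itself. Arm 1 patients are selected for a renal mass, so many within-patient differences may be zero and the rest small. With 10 pairs of that kind the t distribution is a rough approximation, and the p-value can fall below 0.05 where an exact paired test cannot.

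At stake is a p-value in the pilot report that could be carried into the planning of larger studies as evidence that fluorescence finds more disease.

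**Working it through.** **The plan's own figure.** The documents give no power or effect size for this test. The only calculated figure in section 12.3 is the 88% chance of seeing a toxicity of rate 0.10 in 20 patients: 1 − 0.9^20 = 0.878, which agrees.

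**Inputs.** n = 10 per arm, or 20 if pooled (section 12.3). Two-sided 0.05 is assumed, because none is stated. d is the fluorescence count minus the visible/tactile count for one patient.

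**Step 1: t-test against exact test.** Let k patients have d = +1 and the rest d = 0. Then t = √[k(n − 1)/(n − k)] on n − 1 degrees of freedom. The exact two-sided sign or sign-flip p-value is 2 × 0.5^k.

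| k | t, n=10 | t-test p, n=10 | t-test p, n=20 | exact p |
|---|---|---|---|---|
| 3 | 1.96 | 0.081 | 0.083 | 0.25 |
| 4 | 2.45 | 0.037 | 0.042 | 0.125 |
| 5 | 3.00 | 0.015 | 0.021 | 0.0625 |
| 6 | 3.67 | 0.005 | 0.010 | 0.031 |

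For example, k = 4 and n = 10 gives √(4 × 9/6) = 2.45. The t-test needs 4 such patients to reach 0.05; the exact test needs 6.

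**Step 2: is the t-test too liberal overall?** Take d = +1 or −1 with probability q/2 each, otherwise 0, and enumerate all outcomes for q from 0.1 to 0.7. The type I error is 0.0015 to 0.053 at n = 10 and 0.014 to 0.057 at n = 20, so about nominal or lower.

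Given the number of patients who differ, it is 0 for 1 to 3, 0.125 for 4, 0.0625 for 5, 0.031 for 6 and 0.016 for 7. It is again above 0.05 for 8 (0.070), through a seven-to-one split: at n = 10, t = 0.6/√(0.4889/10) = 2.71 against a critical value of 2.26, while the exact p is 2 × (1 + 8)/2^8 = 0.070.

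Unequal differences can reverse the direction. With d = (1,1,1,1,10, rest 0) and n = 10, the t-test gives 0.182 and the permutation test 0.0625.

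**Step 3: false positives alone.** Suppose fluorescence adds no true lesion, and each patient has probability f (assumed) of one benign fluorescence-only mark. From step 1, the t-test is significant when at least 4 patients have one, and the exact test when at least 6 do. The chance is the binomial tail, P(X ≥ 4) or P(X ≥ 6), with X ~ Bin(n, f).

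| f | t-test, n=10 | exact, n=10 | t-test, n=20 | exact, n=20 |
|---|---|---|---|---|
| 0.2 | 0.12 | 0.006 | 0.59 | 0.20 |
| 0.3 | 0.35 | 0.05 | 0.89 | 0.58 |
| 0.4 | 0.62 | 0.17 | 0.98 | 0.87 |

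An exact test on the same raw marks lowers these chances but does not remove the problem. If only confirmed lesions are counted, each benign mark contributes zero.

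**The case against.** The strongest reply is that the test is filed under agreement, and comparing raw marks is a fair agreement question. A reader might infer that the plan scores a higher fluorescence count as better detection. It does not say so. The benefits section (5.1.2) does present more lesions found as an advantage, but it describes a different folate dye in ovarian cancer and adds that OTL38 would have to be studied. What remains is that a paired t-test measures a directional mean difference, not agreement, so its result is open to that reading.

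The second reply is that section 12.7 already handles false positives. A reader might infer that the trial would miss them. That is not supported: a benign excised spot lowers specificity and positive predictive value in the same report. Those estimates cover excised lesions only, however. Section 8.3.2.2 leaves excision to the investigator and asks for the reason when a remaining lesion is left. A spot left in place can therefore enter the t-test count and never reach the two-by-two table. Neither analysis corrects the other.

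The third reply is that the t-test is not generally liberal. Step 2 confirms this, and it stands. Nor is an exact test a rescue when every difference is zero: the t-test is then undefined, but a sign or signed-rank test has no information either.

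Finally, kidney uptake need not add marks. The schematic records suspect tumor lesions, and Appendix A has its own items for background kidney fluorescence. The documents show that false-positive marks are foreseeable, not how frequent they will be.

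**Conclusion.** The point holds, with limits. As written, the test in section 12.8 uses unconfirmed marks, and false positives alone can make it significant: probability 0.12 to 0.62 at n = 10 for assumed per-patient rates of 0.2 to 0.4, and 0.59 to 0.98 if the arms are pooled. These rates are illustrations; the documents give none.

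The choice of test is a smaller matter. The clearest disagreement is 4 or 5 patients who each differ by one lesion in the same direction (0.037 against 0.125; 0.015 against 0.0625). That small differences will predominate is also an assumption. The stronger reading, that the t-test overstates significance whenever few patients differ, fails: with 1 to 3 patients at one lesion each it cannot reach 0.05, and one large difference can make it understate.

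The impact is modest. This is a supplementary analysis of one secondary endpoint in a 20-patient pilot, and no decision hangs on it. The only forward criterion, in section 12.3, is 70% sensitivity.

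**What to change.** Reword the sentence in section 12.8 along these lines:

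- For each arm separately, compare per patient the number of histologically confirmed RCC lesions found by visible/tactile means with the number found by fluorescence, using an exact sign or signed-rank (permutation) test. State the level and sidedness, or call the result descriptive. If every difference is zero, report that and do no test.
- Report per patient, separately, fluorescence-positive lesions that were benign on pathology and those that were not excised and so remain unverified.
- Say whether lesions seen only at the post-excision fluorescence check (marked P) enter the fluorescence count.
- Keep the raw mark counts, if wanted, as a descriptive summary beside kappa.

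The cost is mainly analysis-plan wording: the marks, the pathology on excised lesions and the reasons for not excising are already to be recorded, and surgery does not change. The downsides are larger p-values (at least 6 patients differing in one direction are needed for p<0.05 when none differs in the other), fewer counted lesions, and no verification of unexcised spots. The separate unverified category shows that last gap but cannot close it.

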13 DATA FORMS AND SUBMISSION SCHEDULE

Individual patient registration will be done in the OnCore[®] database. The OnCore[®] database is a comprehensive, web-based, Clinical Trial Management System (CTMS) which utilizes an Oracle database. OnCore[®] was developed by Forte Research Systems, Inc. and is used by the IUSCC Clinical Trials Office (CTO) and supported by the Indiana Clinical and Translational Sciences Institute (CTSI). OnCore[®] properly used is compliant with Title 21 CFR Part 11.

OnCore[®] provides users secure access with unique IDs/passwords and restricts access by assigned roles, from any location, to record, manage, and report on data associated with the operation and conduct of clinical trials.

All source documents are to remain in the patient's clinic file. All documents should be kept according to applicable federal guidelines. Clinical trial data in OnCore[®] are periodically monitored by the IUSCC Data Safety Monitoring Committee (DSMC).

REDCap Database

This study will utilize electronic Case Report Form completion via the secure, web-based, Research Electronic Data Capture (REDCap) system for data input. REDCap was developed by Vanderbilt University and is provided by Indiana University through their community license. REDCap is managed by the Indiana University Department of Biostatistics and secured by University Information Technology Services Advanced IT Core. Access to the password protected database will be limited to the investigators of this study, and any data that is distributed will be either de-identified or authorized by written permission from the subject.

14 PATIENT CONSENT AND PEER JUDGEMENT

The protocol and informed consent form for this study must be approved in writing by the appropriate Institutional Review Board (IRB) prior to any patient being registered on this study.

Changes to the protocol, as well as a change of principal investigator, must also be approved by the Board. Records of the IRB review and approval of all documents pertaining to this study

must be kept on file by the investigator and are subject to inspection at any time during the study. Periodic status reports must be submitted to the IRB at least yearly, as well as notification of completion of the study and a final report within 3 months of study completion or termination.

The study will be conducted in compliance with ICH guidelines and with all applicable federal (including 21 CFR parts 56 & 50), state or local laws.

15 DATA AND SAFETY MONITORING PLAN

Investigators will conduct continuous review of data and patient safety. **Monthly review meetings** for moderate risk trials are required and will include the principal investigator, clinical research specialist and/or research nurse (other members per principal investigator's discretion). **Monthly** meeting summaries should include review of data, the number of patients, significant toxicities as described in the protocol, and responses observed. Summaries will be submitted and reviewed monthly by the DSMC (**Appendix H**). Submit to [contact].

15.1 Study Auditing and Monitoring

All trials conducted at the IUSCC are subject to auditing and/or monitoring. Reports will be reviewed by the full DSMC at the time of study review (Reference Risk Table in full DSMC Charter).

